Official Title of Study: CPAP to Improve Swallow Function Post Total Laryngectomy

NCT# 03328702

Document Date May 20, 2016

Attached is the UC Davis IRB approved Protocol and there have been no protocol changes since 2016.

Sincerely,

A handwritten signature in black ink, appearing to read "[name]".

[name]., M.P.H., Ph.D.

Department of Otolaryngology Head and Neck Surgery

University of California, Davis School of Medicine

PROTOCOL TITLE: Utilization of Continuous Positive Airway Pressure to Improve Swallow Function in Patients Post Total Laryngectomy

1) Protocol Title

Utilization of Continuous Positive Airway Pressure to Improve Swallow Function in Patients Post Total Laryngectomy

Version date: 5.3.16

2) Objectives

To determine whether use of Continuous Positive Airway Pressure (CPAP) can improve the swallow function in patients who underwent total laryngectomy and are experiencing difficulty swallowing.

3) Background

Total laryngectomy is a procedure that involves surgical removal of the larynx and separation of the digestive and airway tracts. The procedure is typically conducted for cases of laryngeal cancer and intractable aspiration. Following this procedure, patients are no longer at risk for aspiration; however some patients continue to experience difficulties in propulsion of food or drink throughout the pharynx. These difficulties can result from pharyngeal neuromuscular damage caused by surgery and radiation (1). Previous research has demonstrated a reduction in pharyngeal contractile pressure and increased pharyngeal transit time in patients post laryngectomy (2,3). Continuous Positive Airway Pressure (CPAP) may assist bolus propulsion in these patients by increasing pressure in the direction of bolus flow. This study aims to evaluate the utility of a CPAP mask to improve pharyngeal swallow outcomes in patients with dysphagia following total laryngectomy. This specific population could be well-suited for this application, since the digestive tract and airway are completely separate and there is no risk of the aspiration into the airway.

PROTOCOL TITLE: Utilization of Continuous Positive Airway Pressure to Improve Swallow Function in Patients Post Total Laryngectomy

4) Inclusion and Exclusion Criteria

Inclusion criteria:

- Age \geq 18 years.
- Patients at least 2 months after total laryngectomy undergoing a dynamic swallow study (DSS).

Exclusion criteria:

- Patients with 100% neopharyngeal stenosis
- Patients with active cancer within 2 months of the study
- Patients with pharyngocutaneous fistula
- Vulnerable population:
 - Adults unable to consent
 - Individuals who are not yet adults (infants, children, teenagers)
 - Pregnant women
 - Prisoners

5) Study Timelines

The subjects will be in study from the time they sign the consent form to completion of the videofluoroscopy study. Approximately 5 additional minutes will be added to each subject's clinical DSS study, with no more than 1-2 seconds of additional fluoroscopic exposure. The estimated date of complete of the study will be 12 months after IRB approval.

6) Study Endpoints

Primary endpoint of the study is complete videofluoroscopic data for all 10 patients.

7) Procedures Involved

Each subject will undergo a standard DSS for the purpose of medical diagnosis. The research study portion will be incorporated into the procedure for patients who consent to participation in the study. The dynamic swallow study is a radiologic examination of swallowing function using fluoroscopy. Standard examinations consist of multiple radio-opaque boluses of different consistencies. During a standard videofluoroscopic study, subject are asked to

PROTOCOL TITLE: Utilization of Continuous Positive Airway Pressure to Improve Swallow Function in Patients Post Total Laryngectomy

swallow barium-coated foods of the following volumes and consistencies in side and front view. Swallows can be added to the protocol in order to assess clinical questions relevant to each specific patient.

Lateral Plane

- 1 ml liquid barium (X2)
- 20 ml liquid barium (X2)
- 60 ml thin liquid barium consecutive sips via straw
- 3 ml pudding

Anterior-to-Posterior Plane

- 20 ml liquid barium
- 13 mm barium tablet

In order to minimize exposing participants to additional radiation during this study, the patients will be asked to wear the CPAP mask during standard swallows test for one of the two swallows of the following consistencies in side view:

- 1 ml thin liquid barium
- 20 ml thin liquid barium

One additional 3ml pudding bolus swallow with the CPAP mask will be added in order to compare swallow function of a pudding consistency with and without the CPAP. This additional swallow will add no more than 1-2 seconds of videofluoroscopic exposure time.

8) Data and/or Specimen Management and Confidentiality

The measures explained in the online application will be taken to protect the confidentiality of subjects:

Videofluoroscopic data collected from the above protocol will be analyzed by paired sample T test and repeated measures of analysis of variance. Data will be stored anonymously and securely, accessible with a password available only to participating researchers.

9) Data and/or Specimen Banking

N/A

PROTOCOL TITLE: Utilization of Continuous Positive Airway Pressure to Improve Swallow Function in Patients Post Total Laryngectomy

10) Provisions to Monitor the Data to Ensure the Safety of Subjects

N/A. This study does not pose more than a minimal risk to subjects.

11) Withdrawal of Subjects

Subjects unable to complete the entire protocol may be withdrawn from the study and not included in data analysis.

12) Risks to Subjects

Patients are undergoing the videofluoroscopic procedure as standard of care. One additional swallow will be added to the standard protocol, adding a minimal 1-2 seconds of fluoroscopic exposure time.

The risks of the CPAP device include skin irritation, dry mouth, nasal congestion. These risks are unlikely to occur during this study in which patients will be wearing the mask for only several minutes. Subjects may experience stomach bloating. Subjects may experience discomfort from wearing the mask.

13) Potential Benefits to Subjects

No direct benefit to participating subjects is anticipated.

14) Multi-Site Research

N/A

15) Sharing of Results with Subjects

Results will not be shared with subjects.

16) Prior Approvals

Radiation Use Committee approval was obtained before IRB submission

17) Provisions to Protect the Privacy Interests of Subjects

Subjects will undergo the protocol privately with a limited number of qualified personnel present. Beyond determining eligibility as described above, no personal or medical information will be sought from participants. The procedure will be limited to only what is described in the above protocol. Only qualified research personnel working on the project will access subjects' secure data, which will be password-protected.

PROTOCOL TITLE: Utilization of Continuous Positive Airway Pressure to Improve Swallow Function in Patients Post Total Laryngectomy

18) Compensation for Research-Related Injury

N/A. The study procedure does not pose more than minimal risk to subjects.

19) Economic Burden to Subjects

N/A

20) Drugs or Devices

N/A

References

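### The only endpoint is a data-completion target, so it cannot answer whether CPAP improves swallowing; the planned comparison names no variable, primary bolus or deciding test

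*Combined protocol and SAP*

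**What the plan says.** - **Section 2 (Objectives)** poses an effect question: "To determine whether use of Continuous Positive Airway Pressure (CPAP) can improve the swallow function in patients who underwent total laryngectomy".
- **Section 3 (Background)** puts the aim in similar terms: to "evaluate the utility of a CPAP mask to improve pharyngeal swallow outcomes in patients with dysphagia". It cites reduced contractile pressure and longer pharyngeal transit as findings of earlier research and adopts neither as an outcome of this study.
- **Section 6 (Study Endpoints)** consists of one sentence: "Primary endpoint of the study is complete videofluoroscopic data for all 10 patients". No secondary endpoint is listed.
- **Section 7 (Procedures Involved)** sets up the CPAP contrast. For the 1 ml and 20 ml thin liquids, "the patients will be asked to wear the CPAP mask during standard swallows test for one of the two swallows". One 3 ml pudding swallow with the mask is added "in order to compare swallow function of a pudding consistency with and without the CPAP".
- **Section 8 (Data Management)** holds the whole analysis plan: "Videofluoroscopic data collected from the above protocol will be analyzed by paired sample T test and repeated measures of analysis of variance".

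**The concern.** The endpoint and the objective do not meet. Section 6 is satisfied by ten complete recordings, and such recordings are equally compatible with CPAP helping, doing nothing, or harming in a way that does not stop the swallows. If Section 6 is read instead as a criterion for finishing the study, then the study has no stated outcome.

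The part of the plan that does bear on CPAP leaves three things open: what is measured on the films, which of the three boluses counts, and which of the two methods (or which ANOVA term) decides. Nothing in the documents says that these will be chosen after the films are read. But a reader of the results could not tell a planned finding from a selected one.

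**Working it through.** **Text check, Sections 6 to 8.** One endpoint, containing no swallow measure and no CPAP contrast. Three bolus contrasts (1 ml liquid, 20 ml liquid, 3 ml pudding), none marked primary. Two methods, neither marked primary. No outcome variable named. The finding rests on this check; the figures below only show what it can cost.

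**The plan's own figure.** The sample size of 10 can be neither reproduced nor refuted, because no significance level, power, effect size or SD is given.

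**Assumptions.** n = 10 complete patients; two-sided 0.05; one variable already fixed; normal paired differences with equal SDs and a common correlation r between boluses of 0, 0.5 or 0.8.

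**1. False positives if each bolus has its own unadjusted paired t test and there is no CPAP effect.** With r = 0 the chance of at least one is 1 − 0.95³ = 14.3%. Simulation of correlated paired t tests (400,000 runs) gives 12.9% at r = 0.5 and 10.3% at r = 0.8. One designated test keeps it at 5%. If the choice of variable is open as well, say three variables over three boluses (the three is an assumption), the chance is 1 − 0.95⁹ = 37.0% when independent and about 18% at r = 0.8.

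**2. Power and precision of one paired t test.** The critical value is t(0.975, 9 df) = 2.262 and the noncentrality is d√10, where d is the mean difference over the SD of the differences.

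| d | Power |
|---|---|
| 0.5 | 29% |
| 0.8 | 62% |
| 1.0 | 80% |

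The d for 80% power is 0.996. The 95% CI half-width is 2.262/√10 = 0.715 SD of the differences.

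**3. Effect of the choice of contrast.** With complete data, the CPAP main effect in an ANOVA with factors CPAP and bolus is the same test as a paired t test on each patient's equal-weight average over the three boluses. A check on one simulated data set gave F(1,9) = 0.5497 and t = −0.7414, with t² = 0.5497. In single-bolus SD units, the SD of that average is √((1 + 2r)/3).

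| r | SD of average | One bolus gains 1 SD: d = (1/3)/SD | Power | All three gain 1 SD: d = 1/SD | Power |
|---|---|---|---|---|---|
| 0 | 0.577 | 0.577 | 37% | 1.732 | 99.8% |
| 0.5 | 0.816 | 0.408 | 21% | 1.225 | 93% |
| 0.8 | 0.931 | 0.358 | 17% | 1.074 | 86% |

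A test on the one bolus that gains 1 SD has 80% power at every r. The two analyses can therefore give different answers on the same films, and the plan does not say which one counts.

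**The case against.** **Section 6 is only a completion target, and Sections 7 and 8 carry the effect question.** This is a natural reading, and the within-patient comparison is indeed planned. But on that reading no outcome is stated at all, and the comparison still lacks a variable, a primary bolus and a deciding test. A completion endpoint would suit a feasibility study. This protocol does not call itself one, and its title, objective and aim concern improvement in swallowing.

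**Harm could defeat the endpoint.** This stands as a narrow exception: a patient who could not complete the CPAP swallows would have incomplete data. It does not turn completeness into a measure of swallow function.

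**The 10% to 14% does not measure the main gap.** This is fair. It covers the choice of bolus for one variable and assumes unadjusted tests with any one counting as success, which Section 8 does not state. The missing variable adds to it, but by how much depends on how many variables are considered. The 29%, 62% and 80% describe n = 10 and would be the same under any endpoint wording.

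**Averaging over boluses may be the weaker choice.** Also fair. Suppose all three boluses gain the same raw amount, equal to 1 SD of the two less variable ones. If the third has twice their SD, the power of the main effect is 93%, 72% or 62% at r = 0, 0.5 or 0.8; at three times, it is 72%, 51% or 44%. A test on one less variable bolus has 80%. This is a reason to choose the contrast deliberately, not to leave it open.

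**The study is small and of minimal risk, and may already be finished.** The documents do not settle whether films have been measured. Participants take one extra swallow with added fluoroscopy, and Section 13 foresees no direct benefit to them, so the exposure is justified only by an answer to the question.

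**Conclusion.** The concern holds and should be corrected. The stated endpoint can be met whatever CPAP does, so it cannot answer Section 2, and no other section supplies the missing outcome. That conclusion depends on no assumed number.

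The size of the consequence does rest on assumptions. With one variable, a two-sided 5% level and unadjusted tests, leaving the bolus open raises the false-positive chance from 5% to between about 10% and 14%. With equal SDs, the choice between the CPAP main effect and a single-bolus test can move power from 80% to between 17% and 37% if one consistency alone benefits, or up to between 86% and 99.8% if all three do. None of this shows that 10 patients is the wrong number.

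**What to change.** Replace the Section 6 sentence with wording such as:

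> The primary endpoint is the within-patient difference (CPAP minus no CPAP) in pharyngeal transit time over the three paired lateral boluses (1 ml liquid, 20 ml liquid, 3 ml pudding), tested once, two-sided at 0.05, as the CPAP main effect in the repeated measures ANOVA (factors CPAP and bolus). The CPAP-by-bolus term and the per-bolus paired t tests are secondary. Completeness of the recordings is a separate feasibility endpoint, counted out of all consented patients.

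Transit time is one option, offered because it is the deficit named in Section 3 that films can time. The investigators may prefer another measure, but should name one. If they expect benefit in one consistency only, or very unequal variability across boluses, they should name a single bolus and its paired t test as primary instead.

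Before any film is measured for the study, fix the start and end landmarks and one rule for a bolus that does not clear, the same with and without CPAP. State who is analysed, since Section 11 allows incomplete subjects to be left out and the equivalence with a paired t test needs complete data. If films have already been measured, report the choice of measure, contrast and test as not prespecified.

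**Cost.** Protocol wording, plus timing of 3 boluses × 2 conditions × 10 patients = 60 swallows on films already planned. No swallow, patient or new method is added.

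**Downsides.** The main effect loses power if only one consistency benefits, and in raw seconds the most variable bolus weighs most. A single named bolus says nothing about the other two. Either way, 10 patients give 80% power only for a standardised difference of about 1.0, so the main report should be the mean difference with its 95% CI (half-width about 0.72 SD of the differences).

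### Section 7 does not set whether the CPAP swallow comes first or second in each pair and Section 8 names no order term, so the plan permits an order under which CPAP and position effects cannot be separated.

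*Combined protocol and SAP*

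**What the plan says.** Section 2 gives the aim: "To determine whether use of Continuous Positive Airway Pressure (CPAP) can improve the swallow function" after total laryngectomy. Section 7 supplies the comparison. The standard examination has two 1 ml and two 20 ml liquid swallows in side view, and patients are asked to "wear the CPAP mask during standard swallows test for one of the two swallows of the following consistencies". For pudding there is one standard 3 ml swallow, and "One additional 3ml pudding bolus swallow with the CPAP mask will be added". Each patient therefore contributes three pairs, each with one CPAP and one no-CPAP swallow.

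Section 8 holds the whole analysis plan: the data will be "analyzed by paired sample T test and repeated measures of analysis of variance". It lists no factors. Section 6 states: "Primary endpoint of the study is complete videofluoroscopic data for all 10 patients". No section mentions randomisation, counterbalancing, a fixed sequence, or a record of the order used.

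**The concern.** Two swallows of the same bolus a short time apart need not be exchangeable. Residue, practice or fatigue could each make the second differ from the first. If the mask is always worn for the same member of a pair, the mean paired difference is the CPAP effect plus or minus the whole position effect. It can then show a benefit that is not there or hide one that is.

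These paired differences are the only evidence the plan collects on the Section 2 objective. A habitual order is easy to fall into when a mask is fitted into a routine examination. If that happened in every patient, no later analysis of that pair could undo it.

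**Working it through.** **Inputs from the documents:** 10 patients (Section 6); three pairs per patient (Section 7); paired t-test and repeated-measures ANOVA (Section 8). The plan gives no alpha, SD, effect size or power, so it has no figure to reproduce.

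**Assumptions:** two-sided alpha of 5%; SD of the paired difference = 1; position effect δ = 0.25, 0.5 or 1.0 SD. The paired difference (CPAP minus no CPAP) has mean +δ if CPAP is second and −δ if first, with no true CPAP effect.

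**1. Can the effects be separated within one pair?** The model has 10 patient columns, one CPAP column and one position column: 12 columns for 20 swallows. With one order in all patients the rank is 11 of 12, so CPAP and position are aliased. With a 9/1 or 5/5 split the rank is 12. If k patients have CPAP second, the bias of the unadjusted mean difference is δ(2k − 10)/10: 1.0δ at k = 10, 0.8δ at 9, 0.4δ at 7 and 0 at 5.

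**2. Can the three pairs be separated jointly?** Suppose order is constant across patients. Over three pairs there are 2³ = 8 patterns.
- In 2 patterns all pairs share one order and the effects are inseparable.
- In the other 6, separation requires both effects to be common to at least two boluses taken in opposite orders. For example, with CPAP second, first, second, CPAP may differ at 1 ml if it is the same for 20 ml and pudding and there is one position effect (rank 3 of 3).
- When the requirement fails, a joint model can mislead. Take CPAP second for both liquids and first for pudding, no CPAP effect, and a position effect of 0.5 SD for liquids and 0 for pudding. The mean differences are (0.5, 0.5, 0). A common-effects fit solves c + p = 0.5 and c − p = 0, so it reports a CPAP effect c = 0.25 SD.

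**3. False positive rate of the plain paired t-test, n = 10.** The first row is exact (noncentral t, df = 9, noncentrality δ√10). The others are from 200,000 simulated trials each.

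| CPAP second in | δ = 0.25 | δ = 0.5 | δ = 1.0 |
|---|---|---|---|
| 10/10 | 0.109 | 0.293 | 0.803 |
| 9/10 | 0.084 | 0.181 | 0.475 |
| 8/10 | 0.066 | 0.106 | 0.201 |
| 7/10 | 0.054 | 0.061 | 0.063 |
| 5/10 | 0.044 | 0.030 | 0.007 |

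**4. Could chance produce a near-fixed order?** With a coin toss per patient, a 9/1 or 10/0 split in one pair has probability (2 + 20)/1024 = 0.021. With separate tosses for three pairs, at least one such split has probability 1 − (1 − 22/1024)³ = 0.063. The main risk is habit.

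**5. Order-adjusted test for a single pair.** The estimate is the average of the two order-specific mean differences, with SE = 0.5 × SD × √(1/n₁ + 1/n₂) on n − 2 df. At 5/5 the SE factor is 0.5√0.4 = 1/√10, the same as for the plain test, so only 1 df is lost. The simulated false positive rate is 0.049–0.051 at every split examined. Power at an assumed 1.0 SD CPAP effect:

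| Split | Adjusted | Plain test, same n |
|---|---|---|
| 5/5 | 0.791 | 0.803 |
| 5/4 | 0.725 | 0.748 |
| 4/4 | 0.657 | 0.681 |
| 5/3 | 0.630 | 0.681 |

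At 9/1 the adjusted power is only 0.386, so adjusting a near-fixed order afterwards is a poor substitute for balance.

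**6. Why the coding must be stated.** With order coded 0/1, the tested intercept is the mean of one order group of 5 (noncentrality δ√5, df = 8). It then rejects in about 8%, 17% and 50% of trials with no CPAP effect.

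**The case against.** The strongest reply is that nothing shows a fixed order was used. If staff varied it, even loosely, the problem largely disappears: at 7/10 the false positive rate is close to nominal. The stated primary endpoint is complete data, which order cannot bias, and every rate above rests on an assumed position effect. The ANOVA might also have been meant to include order. The first three points stand, and they limit the concern to fixed or near-fixed orders and to the Section 2 objective. The last does not rescue the plan: the text does not say so, and with one order in every patient such a term could not be estimated within a pair.

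Three stronger readings are tempting but unsupported:
- A reader might infer that CPAP always came second, above all for the added pudding swallow. Section 7 gives that swallow no position, and for the liquids it says only that one of the two is taken with the mask.
- A reader might infer that the results are biased. The documents show only that the plan does not prevent this.
- A reader might infer that, with orders differing between boluses, separation needs effects common to all three. Step 2 shows that two boluses in opposite orders are enough.

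It is also fair to object that counterbalancing does not remove unequal carryover. That stands, and it belongs in the plan as a limitation.

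**Conclusion.** The omission is certain: no order is set, no order term is named, and one order in all 10 patients is permitted. CPAP and position are inseparable in any pair with one order in every patient, and in the joint analysis if all three pairs share that order. Whether bias occurs, and in which direction, depends on the order actually used.

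The size is illustrative only, under the stated alpha and position effects: false positives of 11%, 29% and 80% at 10/10, 8%, 18% and 48% at 9/10, and near 5–6% at 7/10. These figures are not estimates for this trial. Confidence is high for the omission and conditional for the bias. It should be fixed because the remedy is cheap and a fixed order cannot be repaired afterwards.

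**What to change.** **Add to Section 7:** One order per patient (CPAP first or CPAP second, applied to all three pairs) is set by a randomly generated list prepared before enrolment, with 5 patients per order. A replacement takes the withdrawn patient's order. The order actually used is recorded.

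**Add to Section 8:** The repeated-measures model includes patient (random effect, allowing for correlation among a patient's paired differences), CPAP, bolus and swallow position. For a single pair, the CPAP effect is the average of the two order-specific mean differences (order coded +1/−1), tested with the pooled within-order variance on n − 2 df. This also applies when withdrawals under Section 11 leave the orders unbalanced. State that unequal carryover, such as residue, is not removed.

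**If data are already collected:** report the order used, fit the order term if it varied, and state the limitation if it did not.

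**Cost:** a short list, one recorded item and 1 df (single-pair power at an assumed 1.0 SD effect falls from 80.3% to 79.1%; joint-model power was not computed). The swallows and the fluoroscopic exposure are unchanged. Half of the patients would take the first swallow of every pair with the mask. If orders were instead set independently per pair, about 1 − (1/2)³ = 7/8 of patients would have at least one mask-first pair. Mask handling increases within the roughly 5 extra minutes in Section 5. Because the examination is a diagnostic one (Section 7: "Each subject will undergo a standard DSS for the purpose of medical diagnosis"), the site should confirm that this is acceptable.

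### Does naming both a paired t-test and a repeated-measures ANOVA for three CPAP comparisons, with no ranking or multiplicity rule, call for a change to the plan?

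*Combined protocol and SAP*

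**What the plan says.** Section 2 (Objectives) sets one aim: "To determine whether use of Continuous Positive Airway Pressure (CPAP) can improve the swallow function in patients who underwent total laryngectomy". It names no swallow measure and no bolus.

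Section 7 (Procedures Involved) creates the comparisons. For 1 ml and 20 ml thin liquid, patients are asked to "wear the CPAP mask during standard swallows test for one of the two swallows of the following consistencies in side view". For pudding the protocol states: "One additional 3ml pudding bolus swallow with the CPAP mask will be added in order to compare swallow function of a pudding consistency". Each patient therefore contributes three CPAP/no-CPAP pairs.

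Section 8 holds the only statistical text: "Videofluoroscopic data collected from the above protocol will be analyzed by paired sample T test and repeated measures of analysis of variance". It gives no ANOVA factors, no order between the two methods, no significance level and no multiplicity rule.

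Section 6 (Study Endpoints) does not select a comparison, because it concerns data completeness: "Primary endpoint of the study is complete videofluoroscopic data for all 10 patients".

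**The concern.** There is one question, but at least four tests could be read as answering it: a paired t-test for each of three boluses and the CPAP effect in the ANOVA. The sentence in section 8 does not rank them. The pudding swallow is added specifically so that pudding can be compared with and without CPAP, so a separate test for each bolus is a natural reading.

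On that reading, a significant result in any one bolus could be reported as showing that CPAP improves swallowing. A reader could not tell whether it was the intended deciding test or the most favourable of several. The objective is worded as determining whether CPAP helps, and the protocol does not call itself a pilot or exploratory, so that label does not settle the matter.

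**Working it through.** **Inputs from the protocol.** n = 10 (section 6); three pairs per patient (section 7); paired t-test and repeated-measures ANOVA (section 8). The protocol states no alpha, sidedness, effect size or error rate, so there is no planned figure to reproduce.

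**Assumptions for illustration.** Two-sided 0.05 per test; one swallow measure; normal CPAP-minus-no-CPAP differences with equal SD in the three boluses and a common correlation r between boluses; no CPAP effect for the error rates.

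**Reading A: the ANOVA CPAP effect decides and the t-tests follow it up.** Let d1, d2, d3 be a patient's three differences and m = (d1 + d2 + d3)/3. With complete data, the CPAP main effect tested against patient-by-CPAP variation has F = t² on 1 and 9 degrees of freedom, where t = mean(m) / (SD(m)/√10). This is one test, so the error is 5.0% in either direction and 2.5% in favour of CPAP. Simulation gives 4.9% to 5.1% and 2.5%.

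**Reading B: three unadjusted t-tests and the ANOVA effect all count.** For independent boluses and t-tests only:

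- either direction: 1 − 0.95³ = 0.143
- favouring CPAP: 1 − 0.975³ = 0.073

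With correlated boluses, by simulation (400,000 null trials per correlation):

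| r | Any of 3 t-tests, either direction | Plus ANOVA effect, either direction | Plus ANOVA effect, favouring CPAP |
|---|---|---|---|
| 0 | 14.3% | 16.6% | 8.5% |
| 0.3 | 13.8% | 15.0% | 7.5% |
| 0.5 | 12.9% | 13.6% | 6.8% |
| 0.8 | 10.3% | 10.4% | 5.2% |
| 0.9 | 8.7% | 8.8% | 4.4% |
| 0.95 | 7.6% | 7.6% | 3.8% |

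In favour of CPAP this is 3.8/2.5 = 1.5 to 8.5/2.5 = 3.4 times the one-test rate. Nearly all of it comes from the three t-tests. Adding the ANOVA contributes 16.6 − 14.3 = 2.3 points at r = 0 and 10.4 − 10.3 = 0.1 point at r = 0.8.

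**What a written rule would buy.** Holm adjustment over the three t-tests brings the error to 4.9% at r = 0 and 2.8% at r = 0.95. Naming the pooled comparison as deciding gives 5.0%, which is Reading A again.

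**What it would cost.** Take an illustrative effect of 0.7 SD (assumed) with n = 10. The SD of m is √((1 + 2r)/3), which is 0.577 at r = 0 and 0.966 at r = 0.9.

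- All three boluses respond: the pooled noncentrality is 0.7·√10/SD(m), or 3.83 at r = 0 and 2.29 at r = 0.9. Power is about 93% to 53%. One pre-named bolus has noncentrality 0.7·√10 = 2.21 and power 51%.
- Only pudding responds: the pooled noncentrality is (0.7/3)·√10/SD(m), or 1.28 at r = 0 and 0.76 at r = 0.9. Power is about 21% to 10%. Pre-named pudding has 51%, and pudding Holm-adjusted over three boluses has 30%.

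Neither choice of deciding test is better under both patterns, and the protocol does not say which pattern is expected.

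**The case for a change.** The strongest case for a change is that naming two methods does not rank them. An ANOVA controls the error of the overall question only if it decides or gates the t-tests, and section 8 says neither. The error figures above hold up on repeated simulation. Ranking the comparisons would take only wording: no new patients, swallows or radiation. A clear statement that everything is exploratory would also remove the ambiguity, and the protocol does not make one.

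The textual part of this stands: no section ranks the tests or sets a multiplicity rule. What does not stand is that the plan therefore carries an inflated error rate. The inflation belongs to Reading B alone. The same sentence fits Reading A at 5%, and the protocol gives no basis for saying which is likelier. The harm also depends on a future report choosing one favourable bolus, which the plan does not propose.

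The remedy adds little for three reasons. Its preferred test is already contained in the ANOVA. Its outcome would still be a blank, because no swallow measure is named anywhere in the protocol, and comparisons cannot usefully be ranked before there is a measure to compare. It would also raise questions of its own: a patient with a missing pair (section 11 says only that incomplete subjects may be withdrawn), unequal spread between boluses in a raw average, and the CPAP-by-bolus interaction.

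**Conclusion.** No change to the plan follows. The missing ranking is a gap in detail, not an error in a stated rule or figure. An analyst can fill it sensibly from what section 8 already names: read the CPAP main effect as the answer to the objective, at 5%, and treat the per-bolus t-tests as follow-up, adjusted or plainly descriptive.

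The rate of about 8% to 17% in either direction (4% to 8.5% in favour of CPAP) describes one reading only. It rests on an assumed two-sided 0.05, a single measure, normal differences with equal SDs, and correlation between 0.95 and 0. It should not be quoted as the plan's error rate. More than one measure would raise it, but that follows from the unnamed outcome, which is the prior issue. The choice between a pooled test and one pre-named bolus is a trade-off that depends on whether the effect is expected in all consistencies or in one.
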